A. Background and Significance. The proposed research has substantial potential to identify best means to prevent suicide in the most highly vulnerable population: inpatients admitted following a suicide attempt. Below, we describe the importance of treating this population, the importance of testing CBT in this group, and the scientific importance of testing moderators of treatment response.

A.1. The Significance of Treating Suicidal Behavior in Psychiatric Inpatients. Suicide is one of the top 10 causes of death in the US, accounting for 1.6% of all deaths and 11% of deaths among individuals aged 25-44.¹⁰ Among individuals with depressive disorders, there is an 11% mortality rate from suicide.¹¹ The most significant risk factor for suicide is a history of suicide attempts,¹² present in 5% of the adult US population.¹³ The rate of completed suicide within 1 year is nearly 100 times higher among those who have engaged in suicidal behavior than among control subjects.¹⁴ Suicidal behavior, therefore, is the most promising target for reducing risk of completed suicide.

Most of what is known about the treatment of suicidal behavior comes from clinical trials conducted at the outpatient level of care. While these studies (see below) have been highly promising, it is not known whether their results extend to the highest-risk group: psychiatric inpatients who are admitted to hospital following a suicide attempt. Approximately one third of all suicides by individuals with mental disorders occur in the 90 days following hospitalization.¹ A review of nearly 2 million adult psychiatric inpatients found that the suicide rate in the 90 days after discharge for patients diagnosed with depressive disorders was 235.1 per 100,000

person-years, markedly higher than that in the US general population (14.2 per 100,000 person-years).¹⁵ A meta-analytic review found that the post-discharge rate of suicide was an alarming 2078 per 100,000 person-years among patients admitted with suicidal ideation or behavior.¹⁶ We therefore suggest that efforts to reduce rates of suicidal behavior are critical for inpatients that have attempted suicide.

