Participants meeting all inclusion and none of the exclusion criteria will be randomly assigned (using a computer-generated randomization schedule) to either CBT or TAU using stratified block randomization on SUD. We expect, based on pilot data analyses, that approximately two-thirds of patients in each group will be diagnosed with SUD. Patients assigned to CBT will participate in all aspects of their prescribed treatment plan (i.e., TAU) and in addition will receive up to 4 sessions of CBT (depending on length of stay), lasting 1.5 hours for the first session and 1 hour for the remaining sessions, following the manualized protocol described above. Treatment will be conducted by a doctoral-level clinician trained in the manualized procedures. Training will involve reading the manual, reviewing videos from the training conducted by [name] previously at the IOL, reviewing sessions of pilot study participant treatments, participating in mock treatment role-plays, and completing treatment of at least 2 participants under close supervision (i.e., with all sessions reviewed by the supervising psychologist). Audiotapes will be made of each session and transcriptions will be made from a subsample of participants who consented for transcription of their sessions. A psychologist trained in the CBT protocol will review audiotapes of 10% of sessions and will rate treatment fidelity according to a checklist developed in collaboration with [name] and utilized in our pilot study (> 90% treatment fidelity was rated for all pilot participants). Transcriptions may also undergo gualitative coding for content analysis of case conceptualizations and treatment content (e.g., suicide mode features such as the role of substance use in suicide attempts). As preliminary analyses have found over 10% of the study sample identifies as transgender this study provides a unique opportunity to develop understanding of how minority stress relates to suicide risk for transgender patients as well as explore the experience of transgender patients engaged in suicide prevention therapy. We will code themes related to transgender minority stress in suicide attempt narratives and BCBT treatment (e.g., environmental and external events such as discrimination or harassment: social connectedness; psychological vigilance; anticipation of negative events related to gender identity; internalized transphobia, resilience, gender-affirming care, and transitioning). We have obtained funding from the Hartford Hospital Medical Staff to support the additional time required to complete these transcriptions and content analyses ("Reducing Disparities in Suicide Prevention Treatment for Transgender People", [name], PI). Participants assigned to TAU will engage in usual care. For the post-treatment assessment, participants will meet with an independent evaluator (IE; a clinician who is not the patient's treatment provider and is blind to study group assignment) either in person or by phone/videoconference to complete the C-SSRS. The participant will also complete the IAT and self-report measures (ASIQ, DASS, STHS-State, SCS, DTS, Wish to Live\Die, Reasons for Living\Dying, Client Satisfaction) as close to discharge as possible. In the event that patients are discharged prior to completing this assessment, the assessment will be completed by phone and remote data collection as will typically be done for follow-up assessments. After discharge, participants will have a telephone interview each month for 6 months of follow-up. The IE will administer the C-SSRS, IE Medications Interview, and CSI modified interview. In addition, participants will complete the IAT remotely, and the ASIQ, DASS, STHS-State, SCS, DTS, Wish to Live\Die, and Utility of Techniques through REDCap,¹⁰⁴ a secure data management website. When patients are readmitted to one of the study units during the follow-up assessment time period, the follow-up assessment may be conducted on the up with study staff providing

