
computer and phone access in order to complete data collection. Participants will be reimbursed \$50 for each post-treatment/follow-up assessment. IE meetings will also be audiotaped to facilitate monthly IE calibration meetings to prevent against rater drift. Transcriptions will be made from a subsample of participants who consented for transcription of their study meetings. After each interaction between IE and the participant, the IE will complete an IE Assessment of the Blind which tracks if and how IEs became unblinded to condition as well as requires IEs to guess the condition of the participant and rate their confidence.

We recognize that obtaining follow-up data is critical. Therefore, we will take several steps to optimize our ability to collect such data. During the informed consent process, participants will be asked to provide multiple forms of contact including a direct telephone contact and e-mail as well as the back-up numbers of at least two family members or friends in case study staff are unable to reach the participant at the direct number. If study staff is unable to reach the participant for follow-up at all contact numbers provided following no less than three call attempts, then a letter will be sent to the participant requesting that they contact the study staff. If no reply is received from 1 week of mailing the first letter, than a second letter will be sent requesting that the participant contact the study staff and also indicating a date by which study staff will no longer contact them to schedule follow-up calls. If no reply is received by the indicated date, then the participant will be considered lost to follow-up. In an effort to assess suicide attempts and other important outcome variables (e.g., readmission) over the follow-up period, medical records and publicly available death records will continue to be reviewed.

F.6. Data Analytic Plan

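### F.5 stops scheduling all remaining follow-up calls after one failed contact sequence and describes no new attempt at later months; record review fills only part of the gap

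*Combined protocol and SAP*

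**What the plan says.** F.5 (Procedure) sets the schedule: "After discharge, participants will have a telephone interview each month for 6 months of follow-up". At consent, "participants will be asked to provide multiple forms of contact including a direct telephone contact and e-mail", and also "the back-up numbers of at least two family members or friends in case study staff are unable to reach the participant".

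If nobody can be reached at any number supplied, the steps are:

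- "following no less than three call attempts, then a letter will be sent to the participant".
- After one week without a reply, a second letter goes out, "indicating a date by which study staff will no longer contact them to schedule follow-up calls". The protocol does not say how far ahead that date lies.
- "If no reply is received by the indicated date, then the participant will be considered lost to follow-up".

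The section then adds that "medical records and publicly available death records will continue to be reviewed", with suicide attempts and readmission as the stated targets. F.5 also lets a follow-up assessment be done on the ward when a participant has been readmitted to a study unit.

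**The concern.** The rule is not tied to the month that was missed. It ends staff efforts to schedule calls in the plural, and F.5 describes no fresh attempt when the next monthly interview falls due. Someone out of reach for a few weeks around month 1 is therefore handled like someone who has left the study, although nothing shows that they asked to stop.

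Two things are at stake:

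- **Data.** The monthly interview carries the C-SSRS and the service-use questions, which feed all three primary aims. A.1 notes that "Approximately one third of all suicides by individuals with mental disorders occur in the 90 days following hospitalization", so a miss at month 1 gives up the interviews at months 2 and 3 inside that window, as well as those after it.
- **Analysis.** F.6.3 fits mixed models over the monthly time points and relies on data being missing at random. Turning an intermittent miss into dropout removes later observations that would support that assumption. F.6 names no sensitivity analysis for departures from it.

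**Working it through.** **1. What is lost and what is kept after the cut-off**

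- Ideation and intent (Aim 2): the C-SSRS interview (F.2.5) stops, and records do not supply it. F.5 does not say whether the remote ASIQ continues.
- Suicidal behavior (Aim 1): F.2.4 counts interrupted and aborted attempts and preparatory acts as well as actual attempts. Records can show attempts that reach care, and deaths. The other behaviors may never reach care.
- Readmission (Aim 3): F.2.7 pairs an interview with a query of the HHC record, the only record system named. HHC readmissions stay visible. Admissions elsewhere depend largely on the interview, which has stopped.
- Recovery: F.2.4 sets the follow-up C-SSRS window at the past month. An interview at month 4, for example, does not fill months 2 and 3.

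**2. The plan's own figures (F.6.1)**

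For suicidal behavior the inputs are 37% vs 18.5%, two-sided alpha 0.05 and 80% power. With p̄ = 0.2775:

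n = [1.960·√(2 × 0.2775 × 0.7225) + 0.842·√(0.37 × 0.63 + 0.185 × 0.815)]² / 0.185² = 90.8, so 91 per group.

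The unpooled form gives 89 and the arcsine form 90. The stated 90 is reproduced.

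For the continuous outcomes, d = 0.50, alpha 0.025 and 80 per group after 20% dropout give 82.1% power, consistent with the stated claim of more than 80%. The 20% allowance is stated only for these outcomes.

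**3. Months with no attempt (illustration)**

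Planned follow-up is 200 × 6 = 1,200 patient-months. Three assumptions are made: all of the plan's dropout of up to 20% (40 of 200) arises from this rule; each sequence closes before the next monthly call; and first misses are uniform over months 1 to 6.

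- Mean later months with no attempt: (5 + 4 + 3 + 2 + 1 + 0)/6 = 2.5.
- Total: 40 × 2.5 = 100, and 100/1,200 = 8.3%.
- All first misses at month 6: 0. All at month 1: 40 × 5 = 200, or 16.7%.
- With 10% dropout (20 patients): 20 × 2.5 = 50, or 4.2%, with a range of 0 to 100 (8.3%).

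These are months not attempted. They are not months that would have been observed under a different rule.

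**4. How far record review matters (bounds, not forecasts)**

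For a simple comparison of the two proportions, power is 83.7% with 100 per group. It is 74.8% with 80 per group, that is, if 20% contribute no outcome at all.

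Now keep all 100 per group and let records capture a share c of events among the 20% lost. Count uncaptured events as none, and take loss as unrelated to risk. Both rates are then multiplied by 0.8 + 0.2c:

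- c = 0: 29.6% vs 14.8%, power 71.5%.
- c = 0.5: 33.3% vs 16.65%, power 78.1%.
- c = 1: 37% vs 18.5%, power 83.7%.

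The share c is not given in the documents. These figures cover loss from any cause over the whole follow-up, so they exceed what this rule alone could do.

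**The case against.** The case for the current text has real substance.

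- **The sequence is not slight.** It takes at least three call attempts with every number tried, including at least two relatives or friends, and then two letters. Those contacts may know that the participant is in hospital or has moved. This stands.
- **Record review continues.** A reader might infer that all primary-outcome data for the remaining months are lost. The documents do not support that: attempts and readmission are expressly followed through records, and deaths through public records.
- **The text is silent on several points.** A reader might infer that every channel closes for good. The cut-off concerns staff contact to schedule calls. F.5 does not say that the REDCap and IAT links stop, that e-mail goes unused, or that a participant who replies late is refused. Assessment on readmission to a study unit also remains possible.
- **Clinical contact is separate.** F.4 describes post-discharge telephone calls to patients admitted after an attempt. Ending research scheduling does not end those.
- **Later attempts may yield little.** People who answered neither calls nor letters may not answer next month, and repeated calls to relatives about a psychiatric study carry a privacy cost. Both points stand and limit the fix.

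None of this supplies the missing step. The stop on scheduling further calls is written down, a renewed attempt at the next month is not, and records cannot replace the interview content listed under the first step of the check.

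**Conclusion.** The point holds in this form. After one failed sequence, F.5 ends staff-initiated scheduling of every remaining follow-up call and describes no new attempt at later months. Interview data on ideation and intent, on interrupted or aborted attempts and preparatory acts, and on admissions outside HHC are then uncovered for those months, and the one-month recall window prevents recovery later. Attempts that reach care, HHC readmissions and deaths remain partly covered.

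The size is uncertain. The 8.3% (0 to 16.7%) assumes that the full 20% dropout comes from this rule, although dropout can also include withdrawal. The recoverable share is unknown and could be small.

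Two further inferences are tempting but unsupported. One is that contact is often lost because of the outcome events themselves. That link is plausible and would strain the missing-at-random basis of F.6.3, but the documents give neither rates nor reasons for lost contact. The other is that the documents name the 90 days after discharge as the period of greatest risk. A.1 reports a share of suicides and a suicide rate for that period, and applies its highest-risk wording to psychiatric inpatients as a group.

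This is an avoidable loss that is worth correcting. It does not invalidate the trial.

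**What to change.** In F.5:

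- Record a failed contact sequence as a missed assessment for that month only.
- At each later scheduled month through month 6, make a limited new attempt using the participant's own telephone and e-mail, and keep sending the REDCap and IAT links, unless the participant asks to stop.
- Assign lost-to-follow-up status only after month 6.
- Reword the second letter to say that staff will try again at the next scheduled month, and offer a simple way to opt out.

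The cost is a minor amendment, a revised letter template and a few more contact attempts to people who are not responding. To limit the privacy burden, back-up contacts and letters need not be repeated every month.

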F.6.5. Exploratory Implementation Data Analyses. Exploratory implementation metrics will be summarized using descriptive statistics.

G. Strengths and Weaknesses

G.1. Strengths of the Proposed Study. The primary strength of this study is its high-impact focus, in which we aim to prevent suicide in the most highly vulnerable (yet understudied) population: inpatients admitted following a suicide attempt. Relatedly, a major strength is our use of an empirically-supported intervention for suicidal behavior that is ready for broad dissemination within this population following a successful RCT. The outpatient protocol has been tested in a RCT,⁷ and demonstrates the strongest effect of any cognitive-behavioral intervention on suicidal behavior.⁴ Our sample size ensures adequate power to test the study hypotheses. Our multimodal assessment, including implicit associations, will yield a rich database that allows us to test multiple hypotheses about treatment outcomes as well as moderating factors. Finally, the research environment is a significant strength. As part of a large, statewide healthcare system, we are poised, when the aims of the proposed study are met, to disseminate this treatment across hospitals.

G.2. Weaknesses of the Proposed Study. Because of the time-limited nature of inpatient hospitalization, it is noted that not all of the original outpatient treatment protocol⁶ will be used. Rather, this treatment is focused more on the acute issues of crisis stabilization and establishing reasons for living, with decreased (though not absent) emphasis on elements such as emotion regulation skill building. A similar truncated protocol has been found to be efficacious in controlled research in emergency departments¹⁸ and shows good feasibility and initial efficacy in our pilot work (see section E). We also note that because of varying lengths of stay, all patients may not receive the same "dose" of treatment. We considered standardizing length of stay, but opted against this for ethical reasons of providing least restrictive treatment. Our sample size and data analytic strategy will allow us to examine the relationship between number of sessions and treatment outcome.

H. Literature Cited

